2.4. Task

Participants were comfortably seated in a dimly lit room, approximately 100 cm from a 32” 16:9 computer monitor. Visual stimuli were presented using Presentation Software (Neurobehavioral Systems, Albany, CA, USA). A small yellow fixation point (0.15×0.15° of visual angle) on a grey background remained visible at the center of the screen throughout the experiment to maintain gaze stability and minimize ocular artifacts. The experimental task was a variant of a simple detection task, where the participant had to respond as soon as possible to the visual stimuli described above using a response key with their right index finger, regardless of their emotional content.

In each trial, images were presented in full-screen mode (subtending 35.4 x 31.7°) at the center of the display for 350 ms, then the fixation point remained for a randomized inter-stimulus interval ranging from 1200 to 3000 ms. The task was structured into 12 consecutive runs, alternating in emotional valence: 6 runs of negative images and 6 runs of neutral images. Each run contained 60 images of the

same valence. The order of runs (starting with neutral or negative) was counterbalanced across participants to control for sequence effects. Each run lasted about 2 min and 30 sec, resulting in a recording session duration of approximately 35 min, including breaks. For each valence, 360 trials were collected, for a total of 720 trials per participant. This task has been executed during EEG recordings before and after the stimulation session described below.

Stimulation

Following the first task session, participants executed a 15-minute self-administered tactile stimulation session, which differed depending on group assignment. The Exp group performed the BT (Artigas & Jarero, 2014). The posture followed the traditional butterfly hug configuration (Figure 1): participants were seated on a chair and were instructed to cross their hands and rest their fingertips gently over the suprasternal notch, with thumbs crossed and hands positioned just below the clavicles. From this position, they had to alternate bilateral tapping with their fingertips while keeping their eyes closed and mentally focusing on the negative images previously viewed during the task to maintain affective engagement across the session and ensure continuity between the pre- and post-stimulation EEG recordings. This instruction was intended to prevent disengagement from the emotional context during the stimulation interval. The tapping rhythm was modelled on the original Butterfly Hug procedure (Artigas & Jarero, 2014), and was kept consistent across participants, approximating a rate of one tap per second for standardization purposes in the experimental setting. On the other hand, in the Con group, the posture and instructions were identical. However, instead of rhythmic alternate tapping, participants rested their hands in place without movement (static stimulation). The posture-matched static control condition was selected to provide a conservative baseline by maintaining identical posture, environmental setting, and task structure across conditions. This control was designed to minimize confounds related to body position, visual input, and general task demands. Importantly, the present control condition was not in-tended to function as an active motor or attentional control, but rather as a conservative comparison allowing assessment of whether observed changes in affective neural responsiveness exceeded those attributable to time-on-task or repeated exposure alone.

[figure not shown]

Figure 1. Schematic representation of experimental design. At T0, participants performed the task and the State-Trait Anxiety Inventory – State version (STAI-Y1) and the Visual Analogue Scale (VAS) for discomfort. Participants assigned to the experimental (Exp) group performed a 15-minute self-administered bilateral tapping session (Butterfly Tapping), while subjects of the control (Con) group

adopted the same posture without performing any tapping (static position). At T1, participants repeated the task, followed again by the STAI-Y1 and the VAS. During the task, EEG was continuously recorded.

The session was structured into four blocks of 3 minutes each, interleaved with one-minute pauses. This structure provides sufficient exposure to stimulation while minimizing muscular fatigue and maintaining attention. Before the stimulation, the participants rehearsed the alternating pattern until a consistent and relaxed tempo was achieved. No auditory pacing was used during the actual session to preserve a spontaneous rhythm.

Experimental Procedure

The participants were fitted with the EEG cap and received instructions for the upcoming tasks. The experiment followed a pre-post design with three consecutive phases (Figure 1): Baseline assessment (T0), a 15-minute stimulation session, and post-assessment (T1). At both T0 and T1, participants performed the task while the EEG was recorded and completed the STAI-Y1 and the VAS.

EEG Recording and ERP Analysis

During the task, continuous EEG was recorded using BrainProducts GmbH (Gilching, Germany) equipment, including Recorder 1.2 software and three BrainAmp amplifiers. Two of the amplifiers were connected to a 64-channel ActiCap active electrode system, mounted according to the 10-10 International System. EEG data were sampled at 250 Hz and band-pass filtered offline using a second-order zero-phase Butterworth filter (0.01 – 60 Hz) with an additional 50 Hz notch filter. All signals were referenced to the average of M1 and M2 electrodes. Bipolar electrooculographic (EOG) activity was recorded using a third BrainAmp ExG amplifier, with electrodes placed at the outer canthi of left and right eyes (horizontal EOG), and above and below the left eye (vertical EOG). Electrode impedances were kept below 5 k Ω . On average, 6.7 ± 3.4 electrodes were interpolated in the Con group and 6.1 ± 4.2 in the Exp group. Ocular artifacts (blinks and movements) were removed using the Gratton and Coles algorithm (Gratton et al., 1983), and residual noise was excluded via semi-automatic artifact rejection, discarding epochs with amplitudes exceeding ± 70 μ V. After artifact rejection, an average of 8.1% of trials were excluded from the Con group and 6.7% from the Exp group. To measure post-stimulus activity, 1200 epochs were extracted time-locked to stimulus onset, ranging from 200 ms before to 1000 ms after it. The 200 ms pre-stimulus interval served as the baseline. For each subject, ERP waveforms were averaged separately for negative and neutral stimuli. ERP components were identified using the "collapsed localizer" approach (Luck & Gaspelin, 2017), averaging across all groups and conditions to identify the electrodes to include in statistical analysis. Furthermore, to define analysis intervals, the Global Field Power (GFP) was computed. Specifically, the GFP is a reference-free measure that summarizes the overall distribution of electrical activity across the scalp into a single waveform, providing a measure of the global strength of the ERP signal at each time point. It is computed as the root mean square of the voltage values recorded at all electrodes, simultaneously, across the scalp. The main GFP peaks were used to identify the most prominent ERP components, and the time windows were determined by including the intervals in which the GFP amplitude exceeded 80% of the local maximum. Similarly, corresponding electrodes showing at least 80% of the maximum amplitude within each interval were grouped into spatial pools. Two separate GFP waveforms were generated: one based on the grand average of all post-stimulus activity, and another based on the differential waveforms obtained by subtracting neutral from negative trials. While the first waveform displayed multiple peaks, including those corresponding to early and late visual components, the second one highlighted two time-windows with strong affective modulation: Frontal Positivity (188–228 ms) and central LPP (cLPP; 456–552 ms). For statistical analysis, we focused on the components extracted by the difference waves, capturing the emotion-related

modulation of interest. The electrodes included in the analysis were selected according to the scalp distribution of maximal amplitude in this window, averaging all sites whose activity exceeded 80% of the GFP peak. This procedure identified two electrode pools: a frontal cluster including F1, Fz, F2, FC1, FCz, and FC2, and a centro-parietal cluster comprising Cz, C1, C2, CP1, CPz, and CP2, both consistent with the canonical distribution of the LPP component (Hajcak et al., 2010). Mean amplitudes in this time window and pool were extracted for each condition and used in subsequent statistical comparisons.

Statistical Analysis

Prior to statistical testing, the normality assumption for all variables was assessed using the Shapiro–Wilk test. None of the distributions deviated significantly from normality. The assumption of homogeneity of variance was tested using Levene’s test, which confirmed that the data met the criterion for homoscedasticity. The behavioral and psychological measures were analyzed using a 2×2×2 ANOVA, with Group (Exp vs. Con) as a between-subjects factor and Time (T0 vs. T1) and Valence (Negative vs. Neutral) as a within-subjects factor. Furthermore, a 2×2 ANOVA was conducted on the mean amplitudes of the Frontal Positivity and cLPP difference waves, with Group and Time as factors. Effect sizes were reported using partial eta squared (η^2). Where significant main effects or interactions were found, Bonferroni-corrected post-hoc tests were applied. All tests adopted an α threshold of 0.05. Analyses were performed using Statsoft Statistica 12.0 (StatSoft Inc., Tulsa, OK, USA).

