Neural Basis of the Effect of EMDR Therapy

Study Protocol and Statistical Analysis Plan

26/11/2023

Participants

Using the G*Power 3.1.9.7 software (Faul et al., 2009), an a priori power analysis was conducted to determine the required sample size. The analysis was based on a mixed-design ANOVA framework, consistent with the primary hypothesis testing the interaction between Group (experimental vs. control) and Time (pre- vs. post-stimulation). As no previous ERP studies had specifically examined the effects of Butterfly Tapping on LPP modulation, the expected effect size was set to a conventional medium value (Cohen's $f=0.25$), following Cohen's guidelines (Cohen, 1988). The significance level (α) was set at 0.05, and statistical power ($1-\beta$) was set to 0.95. Under these assumptions, the estimated minimal sample size was 36 participants. To account for potential data loss due to EEG artifacts or technical issues, a total of 38 university students and staff were initially recruited.

This power estimation represents a conservative approximation of the effective statistical sensitivity of the study, as it does not explicitly model features known to enhance power in ERP research, including the repeated-measures structure, the use of differential waveforms (negative minus neutral), and the averaging of a large number of trials across spatially defined electrode clusters. From a sensitivity perspective, the final sample size can therefore be considered sufficient to detect Group \times Time interaction effects of small-to-medium magnitude, which is consistent with effect sizes typically reported in studies examining LPP modulation during emotion regulation and affective interventions. Consequently, the study was adequately powered to address its primary neurophysiological hypotheses.

Participants were healthy, aged between 18 and 40 years (mean age = 25.1 years; SD = 3.0) (55% of females) with normal or corrected-to-normal vision. Inclusion criteria required full right-handedness as self-reported (Edinburgh Handedness Inventory; Oldfield, 1971), no history of neurological or psychiatric disorders, and no current use of psychoactive medications. All participants were naïve to the purpose of the study. Data was collected between July 2024 and February 2025. Participants were pseudo-randomly assigned to the experimental (Exp) or control (Con) group, which were balanced for sex and age.

Self-Report Measures

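### The ERP effect test (Group × Time ANOVA) is valid but does not adjust for the T0 value; adjustment would cut variance by about (1−r)/2, with r unreported

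*Combined protocol and SAP*

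**What the plan says.** The Experimental Procedure section sets out three phases: "Baseline assessment (T0), a 15-minute stimulation session, and post-assessment (T1"). EEG, STAI-Y1 and VAS are all collected at both T0 and T1.

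Under Statistical Analysis, "a 2×2 ANOVA was conducted on the mean amplitudes of the Frontal Positivity and cLPP difference waves, with Group and Time as factors". The behavioural and psychological measures go into a separate three-factor ANOVA that adds Valence. No analysis uses a T0 value as a covariate.

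The Participants section names the Group × Time interaction as the primary hypothesis and bases the sample size on it. There, "the expected effect size was set to a conventional medium value" (f = 0.25), "The significance level (α) was set at 0.05" and power "was set to 0.95". From these, "the estimated minimal sample size was 36 participants", and "a total of 38 university students and staff were initially recruited". Assignment is described as pseudo-random and balanced for sex and age; the mechanism and the group sizes are not given. No T0–T1 correlation, standard deviation or variance of change is reported for any outcome.

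**The concern.** In a two-group, pre/post design the interaction F is the square of the t statistic for the group difference in T1−T0. Taking the change score fixes the coefficient on T0 at 1. If r is below 1 and the variances at the two times are equal, the best coefficient is r, so subtracting the whole of T0 adds noise. T0 is recorded before stimulation, so adjusting for it cannot remove a treatment effect.

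Two things are at stake. The first is precision: the data for a tighter estimate are already in hand. The second is chance imbalance. With about 19 per group, the arms may differ at T0, and the change-score estimate is then shifted for the sample actually drawn. Comparability is reported for sex, age and trait anxiety, but not for T0 cLPP, Frontal Positivity, STAI-Y1 or VAS.

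**Working it through.** **Inputs from the documents.** Two groups, two time points, f = 0.25, α = 0.05, target power 0.95, stated N = 36, recruited N = 38.

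**Assumptions.** 1:1 allocation; equal variances at T0 and T1; assignment independent of T0; f defined on the SD at a single time point; r not stated, so a range is shown.

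**The plan's own figure.** For the interaction with m = 2 measurements, λ = f²·N·m/(1−r), with 1 and N−2 degrees of freedom. At r = 0.5 this gives N = 54 for 95% power, and power 0.83 at N = 36. A minimum of 36 appears only with an undisclosed input: four measurements at r = 0.5 (power 0.952), or two measurements at r of about 0.67–0.69. The sample-size statement therefore does not identify r. The design does not either, because different image sets are shown at T0 and T1.

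**Size of effect.** The change-score test has λ = δ²·(N/4)/(2(1−r)), with δ in single-time SDs. Equating this to 2f²N/(1−r) gives δ = 4f = 1.0.

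**Variance ratio.**
- Change score: proportional to 2(1−r).
- T1 adjusted for T0: proportional to 1−r².
- Ratio: (1−r²)/(2(1−r)) = (1+r)/2, so the saving is (1−r)/2.
- Estimating the slope multiplies the adjusted variance by (N−3)/(N−4), which is 35/34 at N = 38.

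A simulation at N = 36 (20,000 runs) gave ratios of 0.662, 0.776 and 0.932 at r = 0.3, 0.5 and 0.8. The formula with its penalty gives 0.670, 0.773 and 0.928.

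**Power at N = 38, f = 0.25.** The adjusted model uses λ divided by the penalised ratio, with 1 and N−3 degrees of freedom. At r = 0.5, for example, λ = 0.0625 × 38 × 2/0.5 = 9.5 for the planned test. The ratio is 0.75 × 35/34 = 0.772, so λ = 9.5/0.772 = 12.3 for the adjusted test.

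| r | Saving, large sample | Saving, N = 38 | Power, Group × Time | Power, adjusted |
|---|---|---|---|---|
| 0.3 | 35% | 33% | 0.72 | 0.87 |
| 0.5 | 25% | 23% | 0.85 | 0.93 |
| 0.7 | 15% | 12% | 0.97 | 0.985 |
| 0.8 | 10% | 7% | 0.997 | 0.998 |
| 0.9 | 5% | 2% | 1.00 | 1.00 |

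These are variance figures. In standard-error terms, the r = 0.5 saving at N = 38 is 1 − √0.772 ≈ 12%.

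**Where the planned test reaches 0.95 at N = 38.** Power is 0.948 at r = 0.65 and 0.953 at r = 0.66.

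**Where the gain ends at N = 38.** Setting (1+r)/2 × 35/34 = 1 gives r = 68/35 − 1 ≈ 0.94.

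**Chance imbalance.** One standard error of the T0 difference with 19 per group is √(2/19) ≈ 0.32 SD. Given that imbalance, the change-score estimate shifts by (1−r) × 0.32, which is 0.16 SD at r = 0.5. That is 16% of the 1.0 SD effect implied by f = 0.25.

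**The case against.** The planned test matches the stated primary hypothesis. Under random assignment it is unbiased with the correct type I error, and the shift from imbalance arises only conditionally on the T0 difference that happens to occur. This stands: the point concerns efficiency and is not an error in the plan.

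A reader might infer that a quarter of the available precision is lost. That figure belongs to r = 0.5, which the documents do not state, and to variance in large samples. A reader might also infer that the trial is below its stated power. That follows only if r is under about 0.66; at r = 0.7 the planned test already has 0.97 at N = 38. Nor can the gain be assumed equal across outcomes, since each has its own r and none is reported. The advantage is also not universal: at this sample size it disappears above r of about 0.94.

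Two further objections stand in part. The benefit assumes assignment unrelated to T0, and the description as pseudo-random does not establish that. Also, data collection to February 2025, the assumption checks and the ANOVAs are all described as done, so replacing the main test now could be a post hoc switch. Neither objection prevents the adjusted estimate from being reported beside the stated test.

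**Conclusion.** The point holds as a low-cost gain in precision. The Group × Time ANOVA on the ERP difference waves leaves T0 unused as a covariate. Adjustment would cut the variance of the effect estimate by about (1−r)/2, and by somewhat less at N = 38. The gain is substantial at low r, which is also where the planned test falls short of 0.95, and negligible at r of about 0.9 or more. Adjustment also removes the conditional bias from chance T0 differences between groups of about 19. The size rests on an assumed r, equal variances, 1:1 allocation and assignment independent of T0. The documents do not support calling the planned test invalid, quoting a single percentage for the loss, or stating without condition that the trial is underpowered.

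**What to change.** For cLPP and Frontal Positivity, fit T1 ~ Group + T0. Report the adjusted group difference with its 95% CI and the observed r, alongside the Group × Time ANOVA. Do the same for STAI-Y1 and VAS, which as described yield one value per time point. Behavioural measures that vary by image category need the Valence term kept, so the simple model does not replace their three-factor ANOVA.

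State how assignment was made and whether it could depend on T0 outcomes. If results have already been seen, label the adjusted analysis as post hoc and keep the stated ANOVA visible.

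Cost: one model per outcome and one residual degree of freedom, with little return if r proves very high.

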To verify the comparability of the two groups, participants completed the trait sub-scale of the State-Trait Anxiety Inventory (STAI-Y2; Spielberger et al., 1971) at the beginning of the experimental session. This 20-item self-report questionnaire evaluates stable personality-related tendencies to experience anxiety across time and situations. Independent samples t-tests confirmed no significant differences between groups ($t < 1$).

To capture transient emotional responses associated with the experimental manipulation, participants completed two tests, the State subscale of the STAI (STAI-Y1; Spielberger et al., 1971) and the Visual Analogue Scale (VAS; Gift, 1989), immediately after the Tasks described below. Specifically, the STAI-Y1 consists of 20 items assessing how anxious the participant feels "at the moment", rated on a 4-point Likert scale ranging from 1 ("not at all") to 4 ("very much so"). It provides a reliable index of momentary anxiety and is sensitive to situational changes, making it well-suited to evaluating the

effects of affective processing interventions. Furthermore, the VAS was used to quantify subjective emotional discomfort related to the negative emotional content of the task. Participants were asked to indicate the intensity of discomfort experienced while viewing the negative images, with endpoints labeled “no discomfort” (0) and “extreme discomfort” (100). The VAS is a well-validated tool for capturing subtle affective changes in a fast and intuitive manner and is particularly useful in protocols involving repeated measures.

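### The primary Group × Time contrast is tested on two ERP components at 0.05 each with no lead component named, so the ERP familywise error is about 7–10%, not 5%

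*Combined protocol and SAP*

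**What the plan says.** The Participants section describes its power analysis as "consistent with the primary hypothesis testing the interaction between Group (experimental vs. control) and Time (pre- vs. post-stimulation". That sentence names a contrast but no outcome. The next one says that no earlier ERP work had looked at Butterfly Tapping and LPP modulation, which is the nearest the text comes to a lead outcome. The section ends in the plural: "the study was adequately powered to address its primary neurophysiological hypotheses".

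In the Statistical Analysis section, "a 2×2 ANOVA was conducted on the mean amplitudes of the Frontal Positivity and cLPP difference waves, with Group and Time as factors". For the other outcomes, "The behavioral and psychological measures were analyzed using a 2×2×2 ANOVA". Two statements govern error control: "Where significant main effects or interactions were found, Bonferroni-corrected post-hoc tests were applied" and "All tests adopted an α threshold of 0.05". No hierarchy, gatekeeping rule or adjustment across components or outcomes is given.

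**The concern.** The one primary contrast has two chances to succeed, and each has the full 0.05. The Bonferroni step cannot limit this. It starts only after an ANOVA effect has passed at 0.05, and it then separates cell means within that one outcome.

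The sample size rests on a single test at 0.05. If only one component reaches significance, the plan gives no basis for saying whether the primary hypothesis was met. Reporting either one as confirmation carries a higher false-positive rate than the stated 5%.

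**Working it through.** **Inputs from the document.** Alpha 0.05 per test; two ERP components, each with a Group × Time test; f = 0.25, power 0.95, minimum N = 36, recruited N = 38.

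**Inputs assumed.** 19 participants per group (group sizes are not stated); equal correlations between tests (none is stated); one behavioural measure (section 2.4 describes only a speeded key press, and the number of measures analysed is not given).

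**Step 1: the plan's own figure.** The document states a sample size but no familywise error rate. Power for a within-between interaction uses λ = f²·N·m/(1−ρ), with df1 = (k−1)(m−1), df2 = (N−k)(m−1) and k = 2 groups.
- With m = 4 measurements and ρ = 0.5: λ = 0.0625 × 36 × 4/0.5 = 18, df = 3 and 102, power 0.952. N = 36 is reproduced.
- With m = 2 (the pre/post contrast described): N = 54 at ρ = 0.5, 40 at ρ = 0.65 and 34 at ρ = 0.70.

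The plan does not state m or ρ. On any of these settings, the figure covers one test at 0.05.

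**Step 2: familywise error for the two ERP tests.** If independent, 1 − 0.95² = 0.0975. For correlated tests, the Group × Time test in a 2×2 mixed design is a two-sided t test on change scores with 38 − 2 = 36 df. This was simulated with 40,000 runs and 19 per group. The last column adds STAI-Y1, VAS and one assumed behavioural measure, for which independence gives 1 − 0.95⁵ = 0.226.

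| Correlation | Two ERP tests | Five tests |
|---|---|---|
| 0 (exact) | 9.75% | 22.6% |
| 0.3 | 9.4% | 21.0% |
| 0.5 | 8.9% | 18.2% |
| 0.7 | 8.4% | 14.8% |
| 0.9 | 7.2% | 10.5% |

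Numerical integration under a normal approximation agrees: 9.1%, 8.4% and 7.0% for two tests at 0.5, 0.7 and 0.9, and 18.3%, 14.8% and 10.2% for five.

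**Step 3: after the fix.** A single primary component, with the other tested only after it succeeds, holds the ERP error at 5%. Holm over two tests requires the smaller p-value to meet 0.05/2 = 0.025. With both nulls true and independent tests, the error is 1 − 0.975² = 0.0494.

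**Step 4: power cost of the first Holm step.** With N = 38, m = 2 and ρ = 0.5, λ = 0.0625 × 38 × 2/0.5 = 9.5 on 1 and 36 df. Power is 85.1% at 0.05 and 76.8% at 0.025.

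**The case against.** The best defence is that LPP modulation is the outcome behind the effect size, so cLPP is the implied primary and its test alone already has a 5% error rate. This stands in part, because it makes cLPP the natural candidate to name. But the plan never names it. Frontal Positivity receives the same ANOVA in the same sentence, and the ERP section describes both electrode pools as fitting the usual LPP distribution. Nor can cLPP be preferred as the component fixed in advance, because both time windows came from the same difference-wave GFP.

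A second defence is that the rates above count false interactions in either direction, and a false finding in one given direction is roughly half as likely. That is correct. However, the ANOVA F tests are non-directional and the plan names no direction, so either sign could be reported.

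A reader might infer more: that all five outcomes form one confirmatory family with an error rate of about 23%. The document does not support that. It attaches the word primary to the neurophysiological hypotheses. The Self-Report Measures section presents STAI-Y1 and VAS as capturing transient emotional responses and does not call them primary. The number of behavioural measures is not stated. Outcomes from the same participants may well be correlated, so 22.6% is the independent-test end of a range that falls to about 10%.

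A reader might also total every F test in every ANOVA. Most of those are main effects, which do not bear on whether tapping worked, so such a total does not measure this problem.

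**Conclusion.** The point holds for the two ERP tests. Followed as written, the plan gives an error rate of about 7–10% for at least one false ERP Group × Time interaction, which is 1.4 to 2 times the nominal 5%. This needs only the stated alpha and the count of two components; the assumed correlation moves the figure within that range.

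The wider figure of about 10–23% is conditional. It applies only if STAI-Y1, VAS and one assumed behavioural measure are also read as confirmatory, which the plan does not say.

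Timing limits the remedy. The document is dated 26/11/2023, yet it reports data collection up to February 2025, completed assumption checks and time windows derived from the data. It therefore does not show whether any ordering of the components was fixed before the interaction results were seen.

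**What to change.** 1. **If the order was set before the interaction results were seen,** state that Group × Time on cLPP is the single primary test at two-sided 0.05, and that Frontal Positivity is tested at 0.05 only if cLPP is significant. Say when this was decided. Cost: wording only, with no loss of power for cLPP; Frontal Positivity cannot be confirmatory if cLPP fails.
2. **If it was not,** apply Holm across the two ERP Group × Time tests, which needs no ordering, and disclose when the rule was chosen. Cost: the smaller p-value must meet 0.025, with the first-step power loss shown in the working.
3. **In either case,** label STAI-Y1, VAS and the behavioural measures as secondary, either Holm-adjusted or exploratory, and list the behavioural measures analysed.
4. State that a Group or Time main effect alone is not evidence of a tapping effect.

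None of these changes needs new data.
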